To date, several pilot articles have been published in which the authors have demonstrated the feasibility and safety of low-dose irradiation in patients with COVID-19 associated with viral pneumonia [9, 10]. In the article "Low-Dose Whole-Lung Radiation for COVID-19 Pneumonia: Planned Day-7 Interim Analysis of a Registered Clinical Trial", the authors irradiated the entire lung volume with a dose of 1.5 Gy per 1 fraction in

five patients with various concomitant diseases, and the presence of severe respiratory distress requiring oxygen support. Within 24 hours after the session, 3 (60%) patients were removed from auxiliary methods of oxygenation, 4 people (80%) achieved CT-confirmed regression of pneumonia, no acute toxicity associated with radiation therapy was noted [9].

5. Goals and objectives of scientific research.

Objective: To determine the possibility, safety and effects of the use of inhaled low-dose radionuclide therapy in the complex treatment of patients with COVID-19 - associated viral pneumonia.

Tasks:

1. To investigate the dosimetric characteristics of the applied technique on anthropometric phantoms to obtain the coefficients of the transition from the rate of counting pulses over the region of interest to the activity contained in this region (in kBq).
2. To determine the accumulated dose in human lungs during internal irradiation of ^{99m}Tc in a group of healthy volunteers.
3. To develop a methodology for the use of inhaled low-dose radionuclide therapy in complex treatment of patients with COVID-19 - associated viral pneumonia.
4. To assess the possibility of using inhaled low-dose radionuclide therapy in the complex treatment of patients with COVID-19 - associated viral pneumonia.

6. Research design

At the first stage of preparation for the study, to obtain the coefficients of the transition from the pulse count rate over the region of interest to the absolute activity of ^{99m}Tc in the region of interest (in kBq), measurements will be made on a human phantom (see Section 7.3.1).

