At the second stage of preparation for the study to determine the accumulated absorbed dose in the lungs of a volunteer under internal irradiation of ^{99m}Tc after inhalation of UFCNPA, ^{99m}Tc obtained from the TechnegasPlus generator into the crucible of which an activity equal to 833MBq is loaded, a group of 5 volunteers without clinical and radiological signs of pneumonia will be preliminarily formed. For this purpose, at the initial stage, patients from this group will undergo: thermometry and physical examination, as well as X-ray CT of the thoracic organs. In addition, given the importance of immunological criteria in the pathogenesis of Covid-19, it is advisable to assess the immune status and the level of blood cytokines (pro-inflammatory cytokines: TNF α , IL-6, IL-12 TNF- α 4; anti-inflammatory cytokines IL-4, IL-10, TGF β).

In the absence of signs of pneumonia, patients in this group will undergo a single inhalation procedure, followed by a planar scintigraphy on a gamma camera at set intervals (see Item 7.3.2), and an assessment of the cytokine profile 3 hours after the procedure. The modes and geometry of measurements will strictly correspond to the modes and geometry of measurements on the phantom.

The study will enroll women and men aged 18 and over, hospitalized with a diagnosis of moderate new coronavirus infection (COVID-19) and receiving standard therapy.

Classification of COVID-19 by severity [11]:

Average, defined by the presence of at least one of the following signs:

- Fever above 38 ° C;
- NPV more than 22 / min;
- Shortness of breath during physical exertion;
- Pneumonia (susceptible to CT of the lungs);
- SpO2 <95%;
- CRP of blood serum more than 10 mg / l;

It is planned to include at least 10 patients in the protocol of a scientific prospective study.

All patients should undergo:

[figure not shown]
- laboratory test for confirmation of COVID-19 (PCR detection of SARS cov2 RNA);
- X-ray computed tomography of the thoracic organs, in which the presence of viral pneumonia is confirmed;
 - the levels of cytokines in blood plasma were determined (TNF α , IL-6, IL-12 TNF- α E, IL-4, IL-10, TGF β , interferon- γ -inducible protein (IP-10), monocyte chemoattractant protein 1 (MCP-1)
 - an assessment of the immune status was carried out,
 - biochemical indicators (levels of immunoglobulins and CEC) and indicators of the blood coagulation system (hemostasiogram) were evaluated;

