 - the levels of pathogen-specific immunoglobulins A, M, G were assessed (one of the factors in predicting the severity of the course of the disease);
 - output dosimetric control in accordance with the norms of NRB-99/2009 (SanPiN 2.6.1.2523-09).

Traditionally, in LDRT, the level of single doses with an anti-inflammatory effect ranges from 0.5 Gy to 1.0 Gy, and total doses - from 3 Gy to 6 Gy. With another method of dose administration, namely, by inhalation of UFCNPA, ^{99m}Tc, this range can be changed, therefore, the lower level is 10 cGy, and the upper one is 50 cGy.

Based on the dose coefficients, Table 1, presented in the ICRP Publication 128, in the lungs of a standard adult, in accordance with the standard kinetics model of the RFP UFCNPA, ^{99m}Tc, with inhalation of the drug activities of 833 MBq and 4165 MBq, average lung doses will be created internal irradiation equal to 0.1 Gy (10 cGy) and 0.5 Gy (50 cGy), respectively [12]. **Table 1.**

Age	Adult	15 years	10 years	5 years	1 year
Dose cGy / MBq	0,012	0,016	0,022	0,033	0,063

Radionuclide therapy will be carried out no later than one day after CT of the thoracic organs by inhalation of UFCNPA, ^{99m}Tc , carbon nanoparticles with ^{99m}Tc radionuclide attached to them (physical half-life 6.04 hours), by loading the TechnegasPlus 4165 MBq generator into the crucible.

Patients will be transported by specially designated ambulance vehicles using personal protective equipment (goggles, disposable gloves, FFP2 or FFP3 respirator, type 1 anti-plague suit, shoe covers) by the driver and accompanying medical worker. All transported persons are provided with a medical mask. After delivery, the vehicles are disinfected in a specially equipped place on the territory of a medical organization that receives COVID-19 patients (suspected).

Personal protective equipment (goggles, disposable gloves, respirator of the appropriate protection class, type 1 anti-plague suit, shoe covers) will also be used to protect personnel. At the end of the radionuclide therapy session, all surfaces in the room are treated with disinfectants with a virucidal effect, medical waste is collected in special containers for class B waste and disposed of, air disinfection is provided with bactericidal irradiators.

All work on packaging ^{99m}Tc , preparation of UFCNPA, ^{99m}Tc , inhalation of UFCNPA, ^{99m}Tc will be carried out in accordance with the norms of Radiation Standards-99/2009 (SanPiN 2.6.1.2523-09).

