8.2 Exclusion criteria

1. Severe/ extremely severe course of COVID-19 illness, determined by the presence of any of the following signs:

- Acute respiratory failure with the need for invasive respiratory support (tracheal intubation);
- septic shock;
- Multiple organ failure;

2. Life forecast - less than 24 hours, according to the researcher;

3. Forecast of stay in the research center less than 48 hours;

4. The use of another non-standard therapy regimen for the treatment of COVID-19;

5. Established diagnosis of active tuberculosis;

6. Pregnancy or breastfeeding period;

7. Significant diseases or laboratory abnormalities that, in the opinion of the investigator, may increase the risks of participating in the study.

8.3 Criteria for excluding patients from research:

Research subjects will be excluded from further participation in the research in the following cases:

• Revealing, after inclusion of the subject in the study, gross violations of the inclusion / exclusion criteria;

• Withdrawal by the research subject of his consent to participate in the research (despite the fact that the subject has the right not to report the reasons for the withdrawal of the IP, the researcher should make every

possible effort to clarify the reasons for the subject's refusal to participate, for example: the subject does not have an effect from therapy; toxicity / intolerance, etc.);

- Loss to follow-up (this refers to repeated missed visits and inability to contact the subject in other ways. The investigator should make every possible effort to contact the subject and obtain more specific reasons for discontinuing participation, for example: the subject does not feel that the therapy is effective) ; toxicity / intolerance, etc.);

- Termination of the study as decided by local ethics committees or regulatory authorities.

9. Methods and terms of assessment, registration, accounting and analysis of performance indicators.

X-ray CT of the thoracic organs, detailed clinical and biochemical blood tests (ALT, AST, bilirubin, glucose, albumin, creatinine, LDH, CPK, troponin, lactate, ferritin, C-reactive protein, electrolytes), IL-6, NT-proBNP, coagulogram (APTT, prothrombin time, D-dimer), immunogram.

Terms: 1) the evaluation of the clinical results of treatment is carried out during the entire observation period for a limited period of hospitalization of the patient, on the 7th and 14th days after irradiation.

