2) laboratory parameters assessment - during the in-patient period, in accordance with clinical need, but at least 4 times: before the start of RT, in 1, 3, 7 days after irradiation, and before the patient's discharge, cytokine levels - after 3 hours and after 10-12 hours from the procedure.

Table 2.

Methods of assessment	Terms
X-ray CT of thoracic organs	Before treatment, on 7 th and 14 th days after radionuclide therapy, or according to indications
Complete blood count (detailed)	- before treatment - on 1 st and 3 rd days after irradiation, then, according to indications, once every 2-3 days
ALT, AST, bilirubin, glucose, albumin, creatinine, LDH, lactate, electrolytes	- - before treatment - on the 1 st and 3 rd days after irradiation, then, according to indications, once every 2-3 days
CPK, troponin, C-reactive protein, IL-6, NT-proBNP, ferritin, procalcitonin	- before treatment - on the 1 st , 3 rd и 7 th days after treatment after irradiation, then, according to indications,
Coagulogram (APTT, prothrombin time, D-dimer)	- before treatment - on the 1 st , 3 rd и 7 th days after treatment after irradiation, then, according to indications,
Immunogram	- before treatment - on the 1 st , 3 rd и 7 th days after treatment after irradiation, then, according to indications,
Antibodies to SARS cov2 A, M, G	- before treatment - on the 7 th day after treatment after irradiation, then, according to indications,
Cytokine profile	before treatment, 3 hours after the procedure, 12 hours after the procedure, on the 3 rd and 7 th days after irradiation

10. Statistical Analysis Plan

Laboratory indicators were evaluated in accordance with the GLP criteria and with the laboratory standards for them. The assessment of biochemical parameters, the levels of circulating immune complexes and the antibody response to the SARS-cov2 pathogen was carried out on an automatic analyzer AU 480 (Becman Coulter). The hemostasis parameters were evaluated using an ALC Elit PRO automatic analyzer and a TAG 5000 thromboelastograph. The evaluation of immunological parameters was carried out in the direct immunofluorescence reaction with the detection of the results by 6-parameter flow cytometry on the FACS Canto II. Flow cytometry data were processed in the FCS3.0 and Kaluza software applications (Becman Coulter).

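### The objective asks for effects without an untreated comparator, and Section 10 never says what its independent t-test compares; before/after change should be paired, descriptive and not attributed

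*Combined protocol and SAP*

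**What the plan says.** Section 5 gives the aim as "Objective: To determine the possibility, safety and effects of the use of inhaled low-dose radionuclide therapy in the complex treatment of patients with COVID-19". The four tasks listed below it are phantom calibration, lung dose in healthy volunteers, development of the method, and assessment of whether the method can be used in patients. None is an efficacy comparison.

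Section 6 describes the patients as "hospitalized with a diagnosis of moderate new coronavirus infection (COVID-19) and receiving standard therapy", and the number as follows: "It is planned to include at least 10 patients in the protocol of a scientific prospective study". All receive the inhalation, "by loading the TechnegasPlus 4165 MBq generator into the crucible". No control, randomised or historical comparator is described. The only other participants belong to the dosimetry stage: "a group of 5 volunteers without clinical and radiological signs of pneumonia will be preliminarily formed". They also inhale, with 833 MBq loaded. Section 6 calls it advisable to measure their immune status and cytokines at the outset, and then plans "an assessment of the cytokine profile 3 hours after the procedure".

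Section 9 assesses clinical results "for a limited period of hospitalization of the patient, on the 7th and 14th days after irradiation". In Table 2 the patients' cytokine profile is taken "before treatment, 3 hours after the procedure, 12 hours after the procedure", and again on days 3 and 7; other laboratory measures are also repeated in the same patients.

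Section 10 has one inferential method: a t-test for independent samples, with a check of equal variances and pooled and separate-variance forms. It labels differences by p-value thresholds (0.05 and 0.0001). It does not name the groups or time points compared and gives no paired or repeated-measures method.

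**The concern.** There are two linked gaps.

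First, the objective asks about effects, but patients on standard therapy may improve or worsen without the inhalation. Some are also selected on abnormal laboratory values (for example ferritin above 600 ng/ml, Section 8.1) that are then followed in Table 2, so regression toward the mean is possible as well. Without a comparator, a change in CRP, ferritin or IL-6 cannot answer that part of the objective, and no passage limits how a change may be read. Section 1 itself faults most of the older radiotherapy studies for lacking controls or being poorly organised.

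Second, the outcome data in patients are mainly repeated values on the same people, while the one stated test treats its two samples as unrelated. Used that way, it would misjudge the precision of the change.

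**Working it through.** **Inputs.** From the documents: at least 10 patients; 5 volunteers; loaded activity 833 and 4165 MBq; threshold 0.05 (taken as two-sided). The plan gives no effect size, SD, correlation or power, so the figure of 10 cannot be reproduced. Assumptions: one approximately normal marker, equal SDs before and after (unit = 1 SD), an inert treatment, and within-patient correlation ρ of 0, 0.3, 0.5 or 0.7.

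**Step 1. Which contrasts exist?**

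| Contrast | Independent samples? | Can it isolate the inhalation in patients? |
|---|---|---|
| Patients, before v after | No | No: natural course and standard therapy |
| Volunteers v patients, baseline | Yes | No: nobody has inhaled yet; disease differs |
| Volunteers v patients, 3 h | Yes | No: both inhaled; disease and loaded activity differ |
| Volunteers, before v 3 h | No | No: free of recovery from pneumonia, but only 5 people without the disease, at the lower activity |

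**Step 2. Interval width for before/after values, n = 10.**

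Independent formula: t(18) × √(2/10) = 2.101 × 0.447 = 0.940 SD. Averaged over samples this is 0.92 to 0.93, because the sample SD is on average slightly below the true SD.

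Paired formula: t(9) × √(2(1−ρ)) / √10, with t(9) = 2.262. This gives 1.012, 0.846, 0.715 and 0.554 for the four correlations. Averaged over samples: 0.98, 0.82, 0.70 and 0.54.

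**Step 3. Type I error.** The true variance of the mean difference is 2(1−ρ)/n, but the independent test uses 2/n. With ρ > 0 its standard error is too large. Rejection rates below are from 200,000 simulated trials per setting.

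| ρ | Type I error, independent (nominal 5%) | Mean half-width, independent | Mean half-width, paired |
|---|---|---|---|
| 0 | 5.0% | 0.93 | 0.98 |
| 0.3 | 2.3% | 0.93 | 0.82 |
| 0.5 | 1.0% | 0.92 | 0.70 |
| 0.7 | 0.2% | 0.92 | 0.54 |

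The paired test stays at 5% throughout. The two half-widths cross near ρ = 0.1.

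**Step 4. Does pairing solve attribution?** Take an inert treatment and a spontaneous shift of 0.8 SD. Probability of p<0.05 at n = 10:

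| ρ | Independent | Paired |
|---|---|---|
| 0 | 40% | 36% |
| 0.3 | 38% | 48% |
| 0.5 | 37% | 62% |
| 0.7 | 35% | 83% |

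More patients do not help: at n = 20 and ρ = 0.5 to 0.7 the figures are 76 to 80% and 92 to 99%.

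**Step 5. If the test is meant for 5 volunteers against 10 patients.** Noncentral t, df = 5 + 10 − 2 = 13, noncentrality d / √(1/5 + 1/10) = d / 0.548. A difference due to disease alone of 1.0, 1.5 or 2.0 SD reaches p<0.05 in 39%, 72% or 92% of trials.

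**Step 6. Skewed markers.** If a marker is lognormal (log-SD 1, assumed) and falls by one log-SD, a t interval for the mean paired change on the raw scale covers only 84 to 87% at n = 10 for ρ = 0.3 to 0.7, not 95%. A plain mean change is therefore not a safe replacement for every marker.

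**The case against.** The strongest reply is that this is a small uncontrolled pilot, an ordinary design, whose tasks already confine it to dosimetry, method and possibility of use. That stands as far as it goes: the tasks narrow the study. They do not remove effects from the objective, and they do not say how a change may be interpreted.

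A second reply is that Section 10 never says its test is for before/after values, and that a variance-equality check suits two separate groups. This also stands. A reader might infer that the plan applies an unpaired test to paired data; the documents do not show that. What they show is an unnamed comparison. Under the before/after reading the test ignores pairing, and under the volunteers-against-patients reading it compares groups that differ in disease and, after the procedure, in loaded activity.

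Third, a reader might infer that the planned test inflates false positives. With positive correlation it does the opposite, and near zero correlation it is correct. At ρ = 0.3 or more it flags pure recovery less often than a paired test would, so a switch to pairing without a limit on interpretation would make false attribution more frequent.

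Fourth, the 0.8 SD shift is an assumption. It is less plausible at 3 to 12 hours than at day 7, and patients with early signs of a cytokine storm could worsen untreated. The attribution problem runs in both directions; only its size is uncertain.

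Finally, the plan's p-value labels might be read as claims of cause. They grade statistical significance only.

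**Conclusion.** The point holds in this form. Nothing in the plan allows a before/after change in patients to be attributed to the inhalation, yet effects are part of the objective. Section 10 must name its comparison. If that is before/after, the independent test is conservative and its interval too wide: about 0.92 SD against 0.70 or 0.54 SD paired at ρ = 0.5 or 0.7, with no such loss near ρ = 0. Better precision leaves the confounding untouched.

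The contrasts involving volunteers do not fill the gap. The volunteers' own before/3-hour cytokine change, if the baseline sample that Section 6 calls advisable is taken, is worth reporting separately but does not answer the question in patients.

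A reader might go further and infer that the trial is unsound without a control arm. The listed tasks do not require one, so the documents do not support that. All sizes rest on assumed correlations, shifts and distributions; the absence of a comparator and of a named comparison does not.

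**What to change.** 1. Section 5, in line with the listed tasks: *to determine the feasibility, safety and lung dosimetry of the inhalation, and to describe changes in laboratory markers and CT findings.*

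2. Replace the test paragraph in Section 10 with: *For each numerical laboratory measure in Table 2, the within-patient change from the before-treatment value to each scheduled time point is summarised as paired change with 95% CI and the number of patients with both values. Skewed markers such as cytokines, ferritin and CRP are analysed on the log scale (ratio to baseline) or by median paired change. The before/3-hour cytokine change in volunteers is summarised the same way and separately. CT and clinical findings on days 7 and 14 are described by patient. Without a comparator, changes in patients are descriptive and are not attributed to the inhalation.*

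The choice between log scale and median should be fixed for each marker before the data are examined. The significance labels go with the paragraph they belong to.

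Cost: wording in Sections 5 and 10 only; no added patient, visit or sample. The downside is a weaker statement about effects and no p-values.

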Statistical data processing was carried out using the SPSS 2020 program for Windows. The statistical analysis included an estimate of the average values for the sample size, the average value, the minimum and maximum values, the standard deviation, the sum, and the standard error of the average.

To determine the reliability of the differences in the indicators, a T-test for independent variables was used, where for each variable being compared, the sample size, the average value, the standard deviation and the standard error of the average value were compared. For the difference between the means: the average value, standard error, and confidence interval is assumed to be 95%, the significance of the differences is considered reliable at $p < 0.05$ and highly reliable at $p < 0.0001$. The Levin's criterion of equality of variances and the t-criterion of equality of averages for both the combined and separate variances are used.

11. References

4. Burch WM. Evidence for the long-term biological distribution of Technegas particles. *Nucl Med Commun.* 1993;14(7):559-561. doi:10.1097/00006231-199307000-00007.
5. <https://jcsmr.anu.edu.au/research/projects/technegas/clinical-issues-of-technegas-use>.
6. Sampson CB: Adverse reactions and drug interactions with radiopharmaceuticals. *Drug Saf* 8:280-294, 1993.
8. Gaurav Dhawan, Rachna Kapoor, Rajiv Dhawan, Ravinder Singh, Bharat Monga, James Giordano, and Edward J. Low dose radiation therapy as a potential life saving treatment for COVID-19-induced acute respiratory distress syndrome (ARDS). *Calabreseh Radiother Oncol.* 2020 Jun; 147: 212–216.

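### Section 10's independent-samples t-test names no groups; applied to the only two the protocol defines, it could not attribute a difference to the inhalation

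*Combined protocol and SAP*

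**What the plan says.** Section 10 (Statistical Analysis Plan) gives one tool for judging differences in the indicators: "a T-test for independent variables was used", with Levene's test and both the pooled and the separate-variance forms. It adds that "the significance of the differences is considered reliable at" p<0.05, and highly so at p<0.0001. It names no groups, no indicator and no time point.

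The protocol defines two separate sets of people.

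- **Volunteers.** Section 6: "into the crucible of which an activity equal to 833MBq is loaded, a group of 5 volunteers without clinical and radiological signs of pneumonia". Their stated purpose is task 2 of Section 5: "To determine the accumulated dose in human lungs during internal irradiation of ^{99m}Tc in a group of healthy volunteers". Section 6 also calls it advisable to assess their immune status and blood cytokines at the initial stage, and plans a cytokine assessment 3 hours after inhalation.
- **Patients.** Section 6: "It is planned to include at least 10 patients in the protocol of a scientific prospective study". They are in hospital with moderate COVID-19, receive standard therapy, and are treated "by loading the TechnegasPlus 4165 MBq generator into the crucible". Table 2 in Section 9 schedules their cytokines before treatment, at 3 and 12 hours, and on days 3 and 7.

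There is no untreated arm and no arm on standard therapy alone. The objective in Section 5 includes the effects of the inhaled therapy in COVID-19 pneumonia.

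**The concern.** A two-sample test needs two separate sets of people. The only two that the protocol sets up are the volunteers and the patients, and both have cytokines and immune status measured. Nothing in Section 10 keeps the test away from that comparison.

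The comparison says nothing usable about the inhalation. Disease, background therapy and loaded activity all change together from one group to the other, and nobody goes without the aerosol. Correct handling of the variances, or more patients, would not help, because the problem lies in what the two groups are. What is at stake is the reading of the result: a cytokine difference could earn the label *reliable* under Section 10 and then be reported against an objective that speaks of effects.

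**Working it through.** **1. The plan's own figures.** Section 6 gives an adult coefficient of 0.012 cGy/MBq and mean lung doses of 0.1 and 0.5 Gy.

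- 833 × 0.012 = 9.996 cGy, about 0.1 Gy
- 4165 × 0.012 = 49.98 cGy, about 0.5 Gy
- 4165 / 833 = 5.0

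Both stated doses reproduce, and the five-fold contrast in loaded activity is exact. The group sizes come with no effect size, SD or power, so there is no sample-size calculation to reproduce.

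**2. What the two groups can identify.** Code each person by five terms:

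| Group | Intercept | Infection | Standard therapy | Any inhalation | Higher activity |
|---|---|---|---|---|---|
| Volunteers (5) | 1 | 0 | 0 | 1 | 0 |
| Patients (10) | 1 | 1 | 1 | 1 | 1 |

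There are only two distinct rows, so the matrix has rank 2 for 5 parameters. The columns for infection, therapy and higher activity are identical, so their effects cannot be separated. The column for any inhalation equals the intercept, so inhaling at all has no contrast.

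**3. How often the test would be significant with no inhalation effect.** Assume normal data, equal SDs, a two-sided 5% pooled test and exactly 10 patients. Let d be a shift due to disease alone, in SD units. The documents give no SD, so the range for d is assumed.

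- Degrees of freedom: 5 + 10 − 2 = 13
- Noncentrality: d × √(5 × 10 / 15) = 1.826 d
- Probability of p<0.05: both tails of the noncentral t beyond the 5% critical values

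| d (SD) | Noncentrality | P(p<0.05) |
|---|---|---|
| 0.5 | 0.91 | 0.14 |
| 1 | 1.83 | 0.39 |
| 1.5 | 2.74 | 0.72 |
| 2 | 3.65 | 0.92 |
| 3 | 5.48 | 0.999 |

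**4. The test cannot tell the sources apart.** In 40,000 simulated trials, a total shift of 2 SD gave p<0.05 in about 92% (pooled) or 88% (separate variances). The rate was the same whether the shift was all disease, all extra activity, or half of each. A disease shift of 2 SD cancelled by an opposite activity effect of 2 SD gave about 5%. The comparison can therefore mislead in both directions.

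**5. Which cytokines the groups share.** Section 6 lists six legible markers for both groups: TNF-alpha, IL-6, IL-12, IL-4, IL-10 and TGF-beta. The patient list adds two, IP-10 and "monocyte chemoattractant protein 1 (MCP-1"). The only post-inhalation cytokine time that both groups share is 3 hours.

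**The case against.** The strongest reply is that no section announces a volunteer-patient comparison. Section 6 puts the volunteers in a preparatory stage, and task 2 and Section 7.3.2 give them a dosimetry purpose. The test may instead be meant, wrongly, for the repeated measurements within patients. It could also be meant for patient subsets, since Section 8.1 admits people over 65 with or without laboratory signs of a cytokine storm. All of this is correct, so the point must be conditional: *if* the test is applied to these two groups. But a dosimetry purpose stated in Section 6 does not limit what Section 10 tests, and no patient subset is defined for analysis either.

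It is also fair to say that the probabilities show only that a t-test detects a real group difference. They illustrate how easily the label *reliable* could arise without any inhalation effect. They do not predict what this trial will find.

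A reader might infer three stronger things that the documents do not support.

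- **That a significant difference would show disease.** After inhalation, disease, therapy and activity are mixed. The most one can say is that the difference could not be attributed to the inhalation.
- **That the different cytokine lists are a further confounder.** Six markers are shared, and two markers without volunteer values cannot bias a comparison of those six. The gap is missing reference data for IP-10 and MCP-1.
- **That the volunteers are known to be uninfected and off standard therapy.** They are screened by examination and CT. No PCR is listed for them, and their treatment is not described. Both facts are implied only.

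**Conclusion.** The point holds in conditional form and should be corrected. Section 10 leaves its only inferential test without named groups. In the one pair of separate groups that the protocol defines, disease, background therapy and a five-fold loaded activity change together and everyone inhales. A volunteer-patient p-value would therefore be uninformative about the effect of the inhalation, whatever the sample size.

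The size, as an illustration: with no inhalation effect, an assumed disease shift of 1 to 3 SD gives p<0.05 with probability 0.39 to above 0.99. This rests on a two-sided test, normal data, equal SDs, exactly 10 patients and shifts that the documents do not supply. The failure of identification in step 2 does not depend on the shifts, but does take the volunteers to be uninfected and off standard therapy. The documents do not support the claim that the sponsor plans this comparison or intends to read it as efficacy.

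**What to change.** In Section 10:

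1. Name the groups, indicators and time points of every comparison.
2. State that the volunteers are a dosimetry and reference group, and that volunteer-patient differences are not tested or reported as evidence of a treatment effect.
3. Report laboratory indicators as each person's own change from the pre-inhalation value, with a 95% interval for the mean change, separately for volunteers and patients.
4. Show the two groups' 3-hour cytokine changes side by side only descriptively, for the six shared markers, noting that disease, therapy and activity differ together.

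The volunteers' change needs their initial cytokine sample, which Section 6 calls only advisable; that wording should be made definite.

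The cost is a few sentences. No participants are added, treatment is unchanged, and the patient measurements are already in Table 2. The downside is that no between-group p-value can be quoted as an effect. The patients' own change does not replace a control: with no untreated arm it still mixes the inhalation with standard therapy and the natural course of the illness, and the report should say so.

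Adding IP-10 and MCP-1 for the volunteers is optional. It would take 5 × 2 × 2 = 20 assay values (people × samples × markers), provided both samples are taken and enough blood is available, which the protocol does not describe.
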